### 9.3.1. Solicited Events and Symptoms

Systemic solicited adverse events are collected pre-vaccination, and systemic and local solicited adverse events are collected 30 minutes post-vaccination and then daily for 7 days after each vaccination and graded on a scale of 0 (absent), 1 (mild), 2 (moderate) and 3 (severe). See [Table 5](#), [Table 6](#), [Table 7](#), [Table 8](#), and [Table 9](#) for additional grading details. Systemic events include fever, feverishness, fatigue, malaise, myalgia, nausea, dizziness and headache. Local events include pain, tenderness, erythema, induration, ecchymosis, and skin discoloration. If a subject experiences the same local adverse event in both arms for a given vaccination, then the greatest severity between arms will be reported.

The proportion of subjects reporting at least one solicited adverse event will be summarized for each solicited adverse event, any systemic symptom, any local symptom, and any symptoms. The 95% CI calculated using Clopper-Pearson methodology from a binomial distribution (SAS Proc Freq with a binomial option) will be presented. These results are presented in [Table 49](#), [Table 50](#), [Table 51](#), [Table 52](#), and [Table 53](#).

For each systemic and local event, any systemic event, any local event, and any solicited event, the maximum severity over 7 days after each vaccination will be summarized for the Safety population. The number and percentage of subjects reporting each event, as well as the 95% CI calculated using Clopper-Pearson methodology, will be summarized by the maximum severity and vaccination group, separately for each vaccination and over all vaccinations. For each event, the denominator is the number of subjects with non-missing data for the specific event ([Table 54](#), [Table 55](#), [Table 56](#), [Table 57](#), and [Table 58](#)).

The number of subjects reporting each solicited adverse event will be summarized for each day post vaccination for each vaccination and for all vaccinations, both in summary tables starting with [Table 59](#) and ending with [Table 80](#) and graphically starting with [Figure 33](#) and ending with [Figure 42](#).

Solicited adverse events by subject will be presented in [Listing 9](#) and [Listing 10](#).

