- Grade 3 solicited or unsolicited (clinical sign or symptom) adverse event that occurs in the 7 days following study vaccination, lasts for 24 hours or more without decreasing to a Grade 1 or Grade 2, and does not have an alternative etiology. If the subject has a Grade 3 adverse event as per Reactogenicity Tables 3, 4, 5 or 6 in the seven days following study vaccination and it lasts < 24 hours before decreasing to a Grade 2 or Grade 1 adverse event, see discontinuation criteria for Grade 2 below.
- Grade 3 solicited or unsolicited (clinical sign or symptom) adverse event that occurs >7 days following study vaccination and is ongoing at the time of the subsequent study vaccination (i.e., Day 29, Day 57 or Day 169). Conversely, if this Grade 3 adverse event was resolved or reduced to a Grade 1 or Grade 2 adverse event at the time of the subsequent study vaccination, IP may only be given, following the documented determination by the site principal investigator or appropriate sub-investigator, that it would not render study vaccination unsafe or interfere with the evaluation of adverse events or immunologic response.
- Grade 3 clinical safety laboratory value (according to the toxicity table, Section 9.2.2) that does not decrease to Grade 1 or less prior to the follow-up study vaccination (i.e., Day 29,

Day 57 or Day 169). Any clinical safety laboratory parameter may be re-evaluated only once at the local clinical laboratory to assess eligibility prior to the follow-up study vaccination. If the clinical safety laboratory value decreases to Grade 1 or less, the subject may receive the follow-up study vaccination. The study vaccination should be scheduled to occur within the acceptable protocol-specified window for that visit.

- Subjects who experienced any Grade 2 adverse event that is an unresolved Grade 2 or a Grade 1 at the time of the next vaccination, IP may only be given following the documented determination by the site principal investigator or appropriate sub-investigator, that it would not render study vaccination unsafe or interfere with the evaluation of adverse events or immunologic response.
- As deemed necessary by the site principal investigator or appropriate sub-investigator for noncompliance or other reasons.
- Subject refusal of further study vaccination.
- Termination of this trial.
- New information becomes available that makes further administration of the study vaccine unsafe.

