- Pre-administration systemic reactogenicity assessments will be performed prior to study vaccination to establish a baseline. Subjects will then receive the dose of study vaccine via intramuscular injection into the left and right deltoid one after another or simultaneously. The time of administration will be recorded on the appropriate data collection form. Subjects will be observed for at least 30 minutes after the last study vaccination was given. Post-administration local and systemic reactogenicity assessments will be performed. Any AE/SAEs will be recorded on the appropriate data collection form prior to discharge from the clinic.
- Subjects will be provided with a memory aid and other study-related materials to record daily oral temperature, solicited site and systemic AEs, unsolicited AEs, and concomitant medications. Subjects will be encouraged to take their oral temperature around the same time each day. Subjects must not eat or drink anything hot or cold, or smoke within 10 minutes prior to taking oral temperature. Subjects will be instructed on how to use their memory aid and how to measure and record AEs prior to discharge from the clinic. Subjects will be instructed to notify the study center if they develop any severe reactions after study vaccination. If the site principal investigator or appropriate sub-investigator deems the reaction severe enough, further instructions will be given to the subject on the proper course of action, including a return to the clinic for immediate evaluation if appropriate.
- All AEs and SAEs will be collected and recorded on the appropriate data collection form at each clinic visit.

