A full physical examination will be performed on all subjects at the screening visit. This exam will include the following organs and organ systems: general appearance, skin, head and neck, lungs, heart, liver, spleen, extremities, musculoskeletal, lymph nodes and nervous system, by a study clinician licensed to make medical diagnoses and listed on the Form FDA 1572 as the site principal investigator or sub-investigator.

Vital signs (oral temperature, pulse, and blood pressure) will be collected at the screening visit. Subjects must not eat or drink anything hot or cold, or smoke within 10 minutes prior to taking oral temperature. Height and weight will be collected at the screening visit prior to study vaccination.

On Day 1 prior to the study vaccination and at follow-up visits after the study vaccination, a targeted physical examination may be performed, if indicated based on the subject's interim medical history, by a study clinician licensed to make medical diagnoses and listed on the Form FDA 1572 as the site principal investigator or sub-investigator.

On Day 1 and all vaccination visits, vital signs (oral temperature, pulse, and blood pressure) will be collected prior to study vaccination. A urine pregnancy test will be performed within 24 hours prior to study vaccination on all females of childbearing potential. Pre-administration reactogenicity assessments will be performed prior to each study vaccination to establish baseline, then the study vaccination will be given. Subjects will be observed in the clinic for at least 30 minutes after each study vaccination. The study vaccination site will be examined, post-administration reactogenicity assessments will be performed and any AE/SAEs will be recorded on the appropriate data collection form prior to discharge from the clinic. All subjects will receive and complete a subject memory aid from the time of study vaccination through 7 days after study vaccination. Subject memory aids will be reviewed with the subjects for adverse events, (solicited local and systemic AEs and unsolicited AEs) approximately 7 days after each vaccination.

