9 ASSESSMENT OF SAFETY

9.1 Specification of Safety Parameters

Safety will be assessed by the occurrence of:

1. Serious adverse events occurring from the time of study vaccination through approximately 6 months after the last study vaccination.
2. Solicited Adverse Events – reactogenicity events occurring from the time of study vaccination through 7 days after each study vaccination:
 - a) Local AEs including pain, tenderness, erythema (redness), induration (hardness/swelling), bruising and skin discoloration.
 - b) Systemic AEs including fever, feverishness (chills, shivering, sweating), fatigue (tiredness), malaise (general unwell feeling), myalgia (body aches/muscular pain), nausea, dizziness and headache.
3. Clinical safety laboratory adverse events occurring from the time of study vaccination through approximately 7 days after each study vaccination. Parameters to be evaluated include WBC, Hgb, platelet count, ANC, sodium, potassium, Creatinine, total bilirubin and ALT.
4. Unsolicited Adverse Events –non-serious adverse events occurring from the time of study vaccination through approximately 28 days after the last study vaccination.

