11.4.2 Safety Data

Summaries and analysis of safety data will be presented for the Safety Analysis Population.

Solicited AEs will be summarized by severity for each day after vaccination (Days 1-7 post study vaccination) and as the maximum severity over all 7 days. Additionally, solicited AEs will be analyzed by taking the most severe response over the follow-up period, dichotomizing into a binary variable (none versus mild, moderate, or severe) and using standard techniques, such as exact confidence intervals (CI), to summarize the proportion of subjects reporting each symptom, any application site symptom, and any systemic symptom.

Unsolicited non-serious AEs will be collected from the time of first study vaccination through approximately 28 days post last vaccination. Unsolicited AEs will be coded by Medical Dictionary for Regulatory Activities (MedDRA®) for preferred term and system organ class (SOC). SAEs will be collected from the time of first study vaccination through approximately 6 months post last vaccination. The numbers of SAEs are likely to be small in this trial and will be reported by detailed listings showing the event description, MedDRA® preferred term and SOC, relevant dates (study vaccinations and AEs), severity, relatedness, and outcome for each event.

Non-serious unsolicited AEs will be summarized as number and percentage of subjects reporting at least one event in each MedDRA® preferred term and SOC, cross tabulated by severity and relationship to study product. Additionally, the proportion of subjects and exact 95% confidence intervals of AEs in aggregate and by MedDRA® categories will be computed.

Clinical laboratory data will be summarized by severity for each visit, and as the maximum over all post-study vaccination visits. Graphical presentations may include box plots and shift plots.

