### 3.3. Study Definitions and Derived Variables

The term “vaccination group” refers to dose of study product and number of doses that subjects are randomized to receive. Therefore, there are five vaccination groups: ANDV DNA 2mg 3 doses, ANDV DNA 2mg 4 doses, ANDV DNA 4mg 3 doses, ANDV DNA 4mg 4 doses, and placebo. The placebo group will include all subjects who received placebo from all cohorts. Results will also be displayed for all subjects where indicated.

Seroconversion is defined as a post-vaccination ANDV-specific titer  $\geq 40$  if baseline titer  $< 20$  or a minimum four-fold rise compared to baseline if baseline titer  $\geq 20$ .

Geometric mean fold rise (GMFR) represents the geometric mean fold rise in antibody compared to baseline, calculated as the arithmetic mean of the difference in log antibodies back-transformed to the original scale.

Baseline is considered to be the last measurement taken prior to the first vaccination.

The lower limit of quantitation (LLOQ) for both PRT and PsVNA assay results is 20. Any values less than the LLOQ will be assigned a value of 14.1 by the lab. This imputed value will be used for the purpose of calculating summary statistics such as mean and GMT. All corresponding descriptive statistics that are  $< \text{LLOQ}$  will be reported as “ $< 20$ ” in summary tables.

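### The pre-dose symptom grade taken at every vaccination is not used in the incidence and severity tables for solicited systemic events; adding a new-or-worsened count would be a cheap improvement

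*SAP*

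**What the plan says.** Protocol 7.2 and 7.3 require a systemic symptom assessment before the injection at Day 1 and again at Days 29, 57 and 169: "Pre-administration systemic reactogenicity assessments will be performed prior to study vaccination to establish a baseline". Protocol 8.1 repeats this for every dose: "Pre-administration reactogenicity assessments will be performed prior to each study vaccination to establish baseline, then the study vaccination will be given". SAP 9.3.1 confirms the collection: "Systemic solicited adverse events are collected pre-vaccination, and systemic and local solicited adverse events are collected 30 minutes post-vaccination".

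Neither document says how this per-dose baseline enters the counts. Protocol 11.4.2 says that "solicited AEs will be analyzed by taking the most severe response over the follow-up period", split into none versus any. SAP 9.3.1 counts subjects with at least one solicited event (Tables 49-53) and the maximum severity over the 7 days after each vaccination (Tables 54-58). The only general baseline definition, in SAP 3.3, is a single one: "Baseline is considered to be the last measurement taken prior to the first vaccination".

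Pre-dose severity is displayed elsewhere. The by-day tables (Table 59 and those sharing its format) have a Pre-Dose column. The by-day figures (Figure 33 and those sharing its format, including the systemic ones) are to show a pre-vaccination category.

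**The concern.** A baseline is normally collected so that later values can be read against it. The protocol does this for other safety data: a condition present at screening is not an adverse event unless it worsens (9.2.1), and a laboratory value in the Grade 1 range at baseline is reported only if it later reaches Grade 2 or higher (9.2.4). Solicited systemic symptoms have their own pre-dose assessment at four visits but no corresponding rule.

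Fatigue, malaise, headache and myalgia are common complaints. A subject who arrives with mild fatigue and still has it the next day enters Tables 49-58 just as a subject whose fatigue began after the injection does. Alternate etiology does not separate them: Listing 9 carries it only for Grade 3 events (Grades 2 and 3 in sentinel subjects), and carry-over is most plausible at Grade 1.

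At stake is the absolute rate of systemic reactogenicity, part of a primary outcome in a trial whose purpose is estimation. Local symptoms are outside the point, because SAP 9.3.1 collects only systemic symptoms before the dose.

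**Working it through.** **1. The plan's own figures.** The only design calculation is the chance of seeing at least one event, 1-(1-p)^N (Protocol Table 10, SAP Table 3). At p = 5% it gives 1-0.95^10 = 40.1% and 1-0.95^20 = 64.2%, as printed. All 18 cells reproduce to within 0.05 percentage points. Nothing below depends on that table, and the plan gives no figure for symptoms present before dosing.

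**2. Can a symptom be present at dosing?** Yes, within limits.
- Dose 1: exclusion criterion 7 (Protocol 5.2) tolerates minor residual symptoms of a nearly resolved acute illness.
- Doses 2-4: Protocol 5.4.3 foresees a subject whose earlier Grade 2 event is "an unresolved Grade 2 or a Grade 1 at the time of the next vaccination", subject to a documented investigator determination. It also lets a deferral end when symptoms are improving.
- Against this, 5.4.3 withholds a dose when signs or symptoms could confound the reactogenicity assessment, and it defers dosing at 100.0°F or above. Dose 1 requires a temperature below 100.0°F. Carried-over fever is therefore largely prevented; mild subjective symptoms are not.

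**3. Upper bound on subjects affected.** Let p be the share of dosing visits with a systemic symptom already present. Assume p = 2% to 5%, independent across visits; the documents give no value.
- Per dose: at most p, so 2% to 5%, or 0.2 to 0.5 subjects in a group of 10.
- Over four doses, 1-(1-p)^4: 1-0.98^4 = 7.8% and 1-0.95^4 = 18.5%, or 0.8 to 1.9 subjects in 10.
- The result follows the assumption closely: p = 10% would give 1-0.90^4 = 34.4%.

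These are ceilings. A count changes only if the symptom also continues into, or is recorded again in, the 7-day window, and only if the subject would not otherwise have reported it at that grade.

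**4. Effect on a rate and on the contrast.** Let b (no larger than p) be the per-dose share with a symptom both present before the dose and continuing after it. Let t be the true new-onset rate, independent of b. Counted incidence = 1-(1-t)(1-b). With t = 10%:
- b = 2%: 1-0.90×0.98 = 11.8%
- b = 5%: 1-0.90×0.95 = 14.5%

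With the same b in both arms, the vaccine-placebo difference is multiplied by (1-b), that is by 0.98 to 0.95.

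**5. What one carried-over subject does** (exact 95% intervals). Planned sizes are 9 + 1 = 10 per vaccine regimen, 20 per dose level where regimens are pooled, and 4 × 2 = 8 placebo.

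| Group size | No event | One carried-over event |
|---|---|---|
| 8 | 0% (0 to 36.9) | 12.5% (0.3 to 52.7) |
| 10 | 0% (0 to 30.8) | 10% (0.3 to 44.5) |
| 20 | 0% (0 to 16.8) | 5% (0.1 to 24.9) |

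**The case against.** The strongest reply is that the analysis does what the endpoint says. The primary outcome is occurrence of solicited events through 7 days after each vaccination, with no new-onset or relatedness condition, and the SAP follows Protocol 11.4.2. Counting every post-dose symptom errs toward over-reporting, which suits a first-in-human trial. The placebo group is counted in the same way and shows the background. No hypothesis is tested, so no formal conclusion depends on the choice. All of this stands, and it is why the as-reported counts should remain.

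Two stronger readings are tempting, and the documents do not support them.
- A reader might infer from the opening sentence of SAP 9.3.1 that a symptom recorded only before the injection counts as an event. Protocol 9.1 defines solicited events as "reactogenicity events occurring from the time of study vaccination through 7 days after each study vaccination", and SAP 4.4.1 does the same. Tables 49-58 are titled post dose, and the Table 54 footnote restricts severity to post-dosing reports. The sentence is loosely worded, but it does not change the window.
- A reader might infer that the pre-dose data are ignored. They are tabulated and plotted by day for each dose, with placebo shown as well. Those displays are group summaries, however. They cannot show whether the subject with a symptom on Day 2 is the one who had it before the dose.

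**Conclusion.** This is a worthwhile, inexpensive improvement rather than an error. Tables 49-58 leave unused a per-dose baseline that the protocol collects for that purpose, so a symptom that precedes the injection and persists is indistinguishable from a new one in the main summaries. The true size is unknown. The 2-5% per dose and 8-19% over four doses are ceilings that rest on an assumed visit-level rate and independence across visits; the restrictions in Protocol 5.4.3 push the real figure lower. It would be wrong to read them as one to two misclassified subjects in every ten. It would also be wrong to infer a bias between arms: the same rule applies to both, absolute rates are raised, and under the simple model the difference shrinks by only 2-5%. The reason to act is that with groups of 8 to 20 a single carried-over symptom visibly moves a reported rate.

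**What to change.** - Keep the as-reported counts in Tables 49-58 as the primary-outcome summary.
- Beside them, for systemic symptoms only, add the number and percentage of subjects whose symptom was absent before that vaccination or reached a higher grade afterwards than its pre-dose grade at the same vaccination. In Tables 53 and 58, a subject qualifies if this holds at any vaccination.
- State in SAP 9.3.1 that the pre-dose record is never itself counted as an event.
- Note in SAP 3.3 that, for solicited symptoms, baseline is the pre-dose assessment at each vaccination. This reconciles the single definition there with Protocol 7.3 and 8.1.

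No new data are needed. The cost is SAP wording, one extra column and two counts per systemic symptom for the reader. Writing the rule down in advance also avoids choosing it after the results are seen.

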### 9.3.2. Unsolicited Adverse Events

The proportion of subjects reporting at least one unsolicited adverse event will be summarized by MedDRA system organ class and preferred term for each vaccination and over all vaccinations. Denominators for percentages are the number of subjects in the Safety population who received the vaccination being summarized.

Unsolicited adverse events by subject will be presented in [Listing 11](#).

The following summaries for unsolicited adverse events will be presented by MedDRA system organ class, preferred term, dose and vaccination group:

- Incidence and 95% CI of unsolicited adverse events after each dose and any time during the study will be summarized in [Table 81](#), [Table 82](#), [Table 83](#), [Table 84](#), and [Table 85](#);

- The total frequency of unsolicited adverse events after each dose and any time during the study will be summarized in [Table 86](#) and [Table 87](#);
- Summary of severity and relationship to study product after dose 1 and dose 2 ([Table 88](#), [Table 89](#), and [Table 90](#));
- Summary of severity and relationship to study product after dose 3 and dose 4 and at any time ([Table 91](#), [Table 92](#), [Table 93](#), [Table 94](#), [Table 95](#), and [Table 96](#));
- Incidence and 95% CI of unsolicited adverse events related to IP, after each dose and any time during the study will be summarized in [Table 97](#), [Table 98](#), [Table 99](#), [Table 100](#), and [Table 101](#);
- The total frequency of unsolicited adverse events related to IP, after each dose and any time during the study will be summarized in [Table 102](#) and [Table 103](#);
- Subject listing of SAEs ([Table 104](#));
- Bar chart of the total frequency of non-serious related unsolicited adverse events by severity and MedDRA system organ class ([Figure 43](#), [Figure 44](#), [Figure 45](#), [Figure 46](#), and [Figure 47](#));
- Bar chart of the incidence of non-serious related unsolicited adverse events by maximum severity and MedDRA system organ class ([Figure 48](#), [Figure 49](#), [Figure 50](#), [Figure 51](#), and [Figure 52](#));

#### **9.4. Deaths, Serious Adverse Events and other Significant Adverse Events**

A listing of deaths and other serious adverse events will be presented in [Table 104](#), and all moderate or severe, non-serious unsolicited AEs will be listed in [Table 105](#).

